## 1.0 Objectives / Specific Aims

The objective of this study is to investigate whether adding cognitive rehabilitation to an existing occupational therapy (OT) stroke telerehabilitation program will improve stroke survivors' daily functioning.

**Aim: Implement cognitive rehabilitation as a primer for behavioral activation participation-based stroke telerehabilitation to enhance treatment outcomes.** Hypothesis: We expect that this program will improve cognition (both objective and subjective measures), participation, upper extremity (UE) use in real-world activities, and mood/quality of life, generating effect estimates that will inform subsequent larger trials.

## 2.0 Background

An estimated 70% of stroke survivors have persistent cognitive impairment after clinical recovery, commonly in the domains of attention and executive function (e.g., cognitive control, working memory, cognitive flexibility). These multifaceted cognitive deficits are consequential for stroke recovery, with increased severity of cognitive impairment being associated with lower mood and quality of life, limited participation in daily activities, and more protracted disability. Furthermore, post-stroke cognitive impairment (particularly executive dysfunction) may pose a barrier to successful engagement in rehabilitation treatments. Our team developed a behavioral activation participation-based program for stroke survivors that we have successfully deployed in both face-to-face and telerehabilitation settings, led by occupational therapists (OT) and speech language pathologists. We have found that this intervention improves stroke survivors' abilities to participate in real-world home and community activities and reduces depression symptoms. Importantly, we observed that stroke survivors with more pronounced cognitive deficits at enrollment exhibit lowest participation in meaningful real-world activities, highlighting the need for such interventions in this subgroup. To effectively engage in this cognitively demanding telerehabilitation program, which requires metacognitive skills such as self-reflection and problem solving, stroke survivors may benefit from cognitive rehabilitation. Specifically, we propose that addressing cognitive deficits at the outset of this telerehabilitation program (i.e., cognitive priming) will improve stroke survivors' ability to benefit from this intervention by facilitating their learning, planning, organization, and goal management skills. Therefore, the proposed study will employ a titrated design in which we will first deliver sessions of evidence-based cognitive rehabilitation to improve attention and executive function followed by direct application of these new cognitive skills to the existing OT-led telerehabilitation program. Ultimately, we expect that integrating cognitive rehabilitation as a primer will enhance the efficacy of the telerehabilitation program, leading to improved participation in real-world meaningful activities.

## 3.0 Intervention to be studied

Participants will engage in a 10-week study of a stroke telerehabilitation program that incorporates cognitive rehabilitation and occupational therapy (OT). They will complete pre- and post-treatment assessments on weeks 1 and 10 and engage in the 8-week telerehabilitation intervention on weeks 2-9. The intervention consists of 13 telerehabilitation sessions lasting approximately 45–60min each (first 5 weeks: 2 sessions/week; final 3 weeks: 1 session/week). The overall goal of

the program is to improve stroke survivors' participation in home- and community-based activities. This study modifies an existing OT-led telerehabilitation program by adding cognitive rehabilitation to the initial sessions (see Table).

Week	1	2	3	4	5	6	7	8	9	10
Session	PRE	1-2	3-4	5-6	7-8	9-10	11	12	13	POST
Content	Pre Assessment	Cog Rehab	Cog Rehab	Cog Rehab + OT	Cog Rehab + OT	Cog Rehab + OT	OT	OT	OT	Post Assessment.

**Cognitive rehabilitation** will be therapist-led, one-on-one sessions focused on teaching cognitive strategies and their application to a broad set of activities/settings. The cognitive strategies will be in the domains of attention and executive function. The goal is to facilitate cognitive skill learning and generalization, by applying the new cognitive strategies to the participant's performance of home-based and community-based activities (taught through the subsequent OT-led telerehabilitation portion of the intervention). Cognitive rehabilitation interventions have been shown to produce small to medium effect size improvements in function for stroke survivors.

**OT upper extremity rehabilitation** will have 2 components: task-practice and metacognitive strategy training (both described in more detail in Section 10.0). The task-practice aspect of the intervention is considered current 'best practice' in stroke rehabilitation clinics. A task-practice intervention involves a patient repetitively practicing stroke-impaired movement skills within the context of a functional task to promote recovery of the impaired skills. In this study, participants will choose the functional tasks to practice based on the results of the measurement-based process. In addition, task practice sessions will be coached/guided by the therapist through a metacognitive strategy training process which is based on the Cognitive Orientation to Occupational Performance (CO-OP) approach aimed at enhancing self-management during home and community living tasks.

## 4.0 Study Endpoints

We will assess cognition (objective and subjective), functional task performance, activity participation, and psychosocial function with the following measures administered at pre- and post-treatment. Data will be analyzed to observe pre-to post- changes in average ratings of assessments listed in the Table.

Outcome	Instrument
Cognition: Objective	Montreal Cognitive Assessment (MoCA) is a 16-item objective cognitive screening measure. The maximum possible score = 30 points with higher scores indicating better cognition. Scores > 26 are considered unimpaired, scores < 23 indicate cognitive impairment  . Any necessary modifications for remote administration will be made according to guidelines provided on the official MoCA website ( https://mocacognition.com/remote-moca-testing/ ). This may involve saving images of participants' paper-and-pencil responses using screen capture for the purposes of scoring.

Cognition: Subjective	NeuroQoL-Cognitive Function Short Form v.2.0  : 29-item subjective measure of cognitive function. This patient-reported outcome assesses perceived abilities in memory, attention, decision making, or in the application of such abilities to everyday tasks (e.g., planning, organizing, calculating, remembering, and learning) on a 5-item rating scale (1=cannot do to 5=no difficulty). The summed raw score will be converted into a normed T-score (mean=50, SD=10). Higher T-scores reflect better perceived cognitive function.
Functional Task Performance and Activity Participation: Ability for subjects to use the measurement-method to choose appropriately difficult tasks for at home self-directed task practice.	Patient Specific Functional Scale (PSFS)  : a patient-reported measure of task-goal identification and difficulty performing the task on a 0–10-point ordinal scale with higher ratings indicating greater satisfaction with task performance. 
Functional Task Performance and Activity Participation: At home activity performance	Performance Quality Rating Scale (PQRS): The OT observes live performance (via the telerehabilitation video call) of one of the tasks not chosen on the PSFS. Subject's performance is rated by the OT on a 0-10-point ordinal scale with higher ratings indicating greater task performance skill.
Functional Task Performance and Activity Participation: Confidence in own at-home self-management skills	Stroke Self Efficacy Questionnaire (SSEQ)  is a 13-item patient self-report of their confidence (0–10-point Likert scale with higher numbers indicating greater confidence) doing at-home tasks such as using both hands to eat food or prepare a meal for oneself.
Psychosocial Function: Depression	Patient Health Questionnaire (PHQ-9)  : 9-item self-report measure of depression. Items query mood (feeling down, lack of interest), thoughts (guilt, suicidality), and physical symptoms (appetite, sleep, fatigue, concentration, restlessness). Each item is scored on a 4-point scale reflecting how often the symptom has occurred over the last 2 weeks (0=not at all, 3=nearly every day). Scores are summed (out of 27) and analyzed continuously or interpreted via thresholds: 0=no depression, 1-4=minimal depression, 5-9=mild depression, 10-14=moderate depression, 15-19=moderately severe depression, 20+: severe depression.
Psychosocial Function: Functional Impairment	Inventory of Psychosocial Functioning  : 80-item self-report measure of impairment in 7 psychosocial domains within the last 30 days: romantic relationships, family other than spouse/partner, work, friendships and socializing, parenting, education, and self-care. Participants rate the frequency of difficulty on each item on a 7-point scale (0=never, 6=always).
Psychosocial Function: Sleep disturbance and sleep related impairment	PROMIS Sleep Disturbance  : 8-item self-report of perceived difficulties falling and/or staying asleep. Items are rated on a 5-point rating scale (1=no problem, 5=very much a problem). The summed raw score will be converted into a normed T-score (mean=50, SD=10). Higher T-scores reflect more sleep disturbance.

## 5.0 Inclusion and Exclusion Criteria/ Study Population

Eligibility will be determined based on self-report or clinician assessment/determination, when indicated.

### ***Inclusion Criteria***

- i. Have experienced ischemic or hemorrhagic stroke with resultant paresis of one arm/hand at least 30 days prior
- ii. Adults ages 21 years or older
- iii. Are able to speak and read English

- iv. Have corrected vision to be able to read text on a screen
- v. Have a device on which a telerehabilitation visit can be conducted (i.e., phone, tablet, or laptop) and a Wi-Fi connection or cellular service
- vi. Able to participate in the study's assessment sessions as per the judgment of the licensed, experienced stroke telerehabilitation occupational therapist.

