## 10.0 Study Design / Methods

**Design:** This is a quasi-experimental, single group pilot study that investigates the impact of integrating cognitive rehabilitation into an 8-week OT-led activity- and participation-based stroke telerehabilitation program. Participants will attend a total of 15 study visits over 10 weeks. A summary and timeline of procedures are outlined and described in the following table.

**Visit Schedule:** To accommodate participant preference/comfort and feasibility, we have designed the visit schedule to be flexible in the following ways:

- The PRE assessment visit will occur within 1-10 days prior Telerehab session 1 and the POST assessment visit will occur within 1-10 days after Telerehab session 13.

- Given the 2–3-hour length of the PRE session, the participant and therapist may decide to split the PRE procedures over 2 visits if the participant becomes fatigued or has other time constraints.
- We will make an effort to schedule telerehab visits on the days and times of the participants' choosing to the extent that the therapists' schedules permit.
- In extenuating circumstances that lead to cancellations/missed sessions (e.g., serious weather event, illness, holidays):
  - Telerehab sessions may extend into an additional week. This would make the intervention duration 9 weeks instead of 8 and the duration of full participation 11 weeks instead of 10.
  - Make-up telerehab sessions may be added to any intervention week.

Week	Week 1	Weeks 2-3	Weeks 4-6	Weeks 7-9	Week 10
Session	PRE	1-4	5-10	11-13	POST
Mode (session duration)	Virtual (2-3 hrs)	Telerehab (45–75 min/session 2x/week)	Telerehab (45–75 min/ session 2x/week)	Telerehab (45–75 min/session 1x/week)	Virtual (2 hrs)

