## Session “PRE”: PRE-TREATMENT ASSESSMENTS

**Aphasia Screening:** Prior to consent, we will determine whether participants meet exclusion criterion *i* (moderate-severe or severe aphasia) by the following procedures:

1. The therapist will query whether the participant might have symptoms of aphasia: E.g., “Do you have any difficulty communicating with others since your stroke?”

If this question is endorsed or the therapist suspects aphasia based on their interactions, then:

2. The therapist will administer the Language Screening Test (LAST) form A. This 15-item measure tests expressive and receptive language. We will make adaptations to accommodate remote administration when needed. Participants will be excluded from the study if they score:
  - A. Less than 6/7 on the receptive index OR
  - B. Less than 4/8 on the expression index OR
  - C. A total score below 15/15 (but do not meet criteria A or B) and per clinical judgment:
    - For those meeting criterion C, the therapist conducting the assessment will consult with the study SLP to determine eligibility. If the therapist and SLP deem it necessary, the SLP will meet with the participant to do a more thorough evaluation of their aphasia and determine whether they should be included in the study.

**Sample Characteristics:** We will collect the following data at the initial visit that will be used to describe characteristics of the sample:

- Demographics: self-reported age, biological sex, gender, race, ethnicity, time since stroke, stroke location, pain, and stroke severity (NIH Stroke Scale).
- Technological Literacy via a questionnaire modified for stroke telerehabilitation
- The Occupational Therapy Occupational Profile to qualitatively document aspects of the participant’s context that impede/facilitate telerehabilitation including technology (internet, computer) and the physical and social home-context.
- We may also conduct medical chart review to collect the following information: stroke date, NIH Stroke Scale score, and discharge scores on stroke rehab assessments.

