## 11.0 Data Management

**Recruitment Data:** Recruitment records will be housed in REDCap. Only IRB-approved study personnel will have access to the REDCap database while actively enrolling for the study.

Data Analysis: Data from the prospective sample (n=20) will be used to calculate descriptive statistics of all outcome measures collected prior to (pre-treatment) and immediately following (post-treatment) the intervention and the corresponding change scores. The preliminary effect sizes of the proposed intervention will be generated by evaluating 1) change in each outcome measure from pre- to post-treatment and 2) the associations between changes in cognitive measures and changes in the participation and psychosocial function measures. To explore the potential additive benefit of cognitive priming, we will compare change in the participation measures between the prospective sample (n=20) and historical data (n=30) from stroke survivors who have completed the telerehabilitation program without the cognitive rehabilitation primer component.

Confidentiality: All data except for the consent forms and HIPPA forms will be coded at the time of data recording. All electronic data will be stored in a password-protected research server that is accessible to IRB-approved study personnel only. All paper data with personally identifiable information (e.g., the consent forms) will be stored in a key-locked cabinet in a key-locked room that is accessible to IRB-approved study personnel only. Other paper data without personally identifiable information including testing sheets documenting testing sequences and notes will also be stored in a cabinet in a key-locked room that is accessible to IRB-approved study personnel only.

Data sharing: Only de-identified coded data will be reported and/or shared with the public and other investigators in publications, in ClinicalTrials.gov, or via data depository.

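### Section 11 labels uncontrolled pre-to-post change as the intervention's effect size and makes no use of time since stroke, so any spontaneous recovery would be counted in it

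*Combined protocol and SAP*

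**What the plan says.** - **Entry (Section 5.0, Inclusion Criteria, item i).** "Have experienced ischemic or hemorrhagic stroke with resultant paresis of one arm/hand at least 30 days prior". No upper limit is given.
- **Design (Section 10.0).** "This is a quasi-experimental, single group pilot study that investigates the impact of integrating cognitive rehabilitation". There is no concurrent control.
- **Analysis (Section 11.0, Data Analysis).** "The preliminary effect sizes of the proposed intervention will be generated by evaluating 1) change in each outcome measure from pre- to post-treatment". The same sentence adds associations between changes in the cognitive measures and changes in the participation and psychosocial measures.
- **Historical comparison (Section 11.0).** Introduced with "To explore the potential additive benefit of cognitive priming", it says "we will compare change in the participation measures between the prospective sample (n=20) and historical data (n=30) from stroke survivors". The historical group completed the program without the cognitive component. No matching or adjustment is stated.
- **Time since stroke (Section 10.0, Session PRE, Sample Characteristics).** The list collected at the initial visit includes "time since stroke, stroke location, pain, and stroke severity (NIH Stroke Scale"). Stroke date may also be taken from the chart. The stated use is sample description; Section 11.0 does not mention it.
- **Use of the results (Section 1.0).** The effect estimates are to inform later, larger trials.

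**The concern.** In a single group, mean change is the sum of the treatment effect and everything else that moves scores between the two visits: natural recovery, retest effects and regression to the mean. Natural recovery deserves particular attention here because entry opens at 30 days after stroke, the interval between assessments is about two months, and the variable that would show whether change depends on stage of recovery is collected but left out of the analysis.

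The consequence lies downstream. If the pooled change is passed on as an effect size of the intervention, a later trial could be sized on a figure that is partly recovery and so be underpowered. With 20 participants, a few enrolments either way would also change the early share, and the estimate with it.

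**Working it through.** The plan gives no power, precision or effect-size figure (Section 6.0 states only the sample size of 20), so there is nothing to reproduce. The steps below check the timing, the route of the bias and its possible size.

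**1. Timing.** Inputs are from Section 10.0, Visit Schedule: PRE is 1 to 10 days before session 1, POST is 1 to 10 days after session 13, and the intervention lasts 8 weeks (taken as 49 to 56 days between first and last session).
- Shortest interval: 49 + 1 + 1 = 51 days.
- Longest interval: 56 + 10 + 10 = 76 days, or 83 with the permitted extra week.
- A participant assessed at day 30 would have the POST visit between day 30 + 51 = 81 and day 30 + 76 = 106, or day 113 with the extra week. The whole interval lies within the first four months after stroke.
- The PQRS is given at sessions 1, 5 and 13 instead, so its interval is somewhat shorter.

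**2. Pre-to-post change.** Let f be the share of participants still recovering and g their natural change in SDs of the change score, with no natural change in the rest. With no treatment effect, the expected standardised change is f × g. Both inputs are assumptions; the documents give neither.

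| f | g = 0.3 | g = 0.5 | g = 0.8 |
|---|---|---|---|
| 0 | 0 | 0 | 0 |
| 0.2 | 0.06 | 0.10 | 0.16 |
| 0.3 | 0.09 | 0.15 | 0.24 |
| 0.5 | 0.15 | 0.25 | 0.40 |

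These use the SD within each subgroup. Dividing by the SD in the mixed sample, √(1 + f(1 − f)g²), lowers the values slightly: at f = 0.5 and g = 0.8, 0.40 / √1.16 = 0.37.

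The plan names no test. If a two-sided paired t-test at 0.05 were used, simulation at f = 0.5 and g = 0.5 gives p < 0.05 in about 17% of trials with no treatment effect, against 5% at f = 0.

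**3. Historical comparison.** Recovery contributes (f in the prospective group − f in the historical group) × g. It cancels if the mixes are equal. An assumed mix difference of 0.25 to 0.5 with g of 0.3 to 0.8 shifts the contrast by 0.25 × 0.3 = 0.075 to 0.5 × 0.8 = 0.40 SD, in either direction.

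**4. What 20 participants can support.** The 95% half-width for mean change, in SDs of change, is t(0.975, n − 1)/√n.
- All 20: 2.093/4.472 = 0.47.
- A late subgroup of 16, 14 or 10 (early shares of 20%, 30%, 50%): 2.131/4.000 = 0.53, 2.160/3.742 = 0.58, 2.262/3.162 = 0.72.
- Regression of change on centred log time in all 20: the slope per SD of log time has half-width t(0.975, 18)/√19 = 2.101/4.359 = 0.48 residual SD. The intercept is still the pooled mean change.

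Either route is imprecise, but the regression keeps every participant and the pooled figure.

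**The case against.** The strongest defence is that the plan is open about its limits: it calls itself a quasi-experimental, single-group pilot and its effect sizes preliminary. It also has an external comparator, the 30 historical participants, which bears directly on the stated objective of whether adding cognitive rehabilitation helps. Natural recovery cancels there to the extent that the groups are alike in time since stroke.

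Part of this stands. It would be wrong to say that the plan has no comparator. But the comparison is exploratory, concerns the added cognitive component rather than the whole program, and covers participation measures only; the cognitive and psychosocial outcomes have none. Nothing is said about time since stroke in the historical group. The word preliminary does not tell a reader that the figure includes recovery, and Section 1.0 intends the estimates for use.

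Three stronger readings are tempting but not supported:
- **That spontaneous recovery will be reported as the effect.** This needs early entrants, and no distribution of time since stroke is given. Most participants could be long past their stroke.
- **That Tele-OT referrals will be earlier after stroke than registry members.** This is plausible, but Section 8.0 gives time since stroke for neither source.
- **That a late-group estimate should be carried forward instead.** It would rest on 10 to 16 people under the assumed shares, with half-widths of 0.53 to 0.72 SD. It would change the target population while entry stays open from 30 days, and it would still include retest effects and regression to the mean.

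**Conclusion.** The point holds in conditional form. Section 11.0 attaches the name of an intervention effect to uncontrolled change, and the analysis leaves out the recorded variable most relevant to natural recovery. Whatever recovery occurs would be counted in full.

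Its size cannot be derived from the documents. The illustrative 0.06 to 0.40 SD rests on an assumed early share, an assumed natural gain, no natural gain in later participants and a single gain for all outcomes. The last is unlikely to hold across measures as different as the MoCA, sleep disturbance, depression and self-efficacy. I set no benchmark beside it: Section 3.0 describes effects of cognitive rehabilitation as small to medium without figures, and for that component alone.

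This is a matter of labelling and analysis, not a flaw in eligibility or a reason against the pilot. It is worth correcting before results are seen because the estimates are to be reused.

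**What to change.** Leave eligibility unchanged and amend Section 11.0:

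1. Call the pooled figure pre-to-post (10-week) change rather than an effect size of the intervention. State that it includes any natural recovery, retest effects and regression to the mean.
2. Prespecify a descriptive analysis of change against time since stroke, for example regression of change on centred log time since stroke in all 20 participants. Report it with intervals beside the pooled figure, not in place of it.
3. Report the distribution of time since stroke in both groups of the historical comparison. Where the historical records hold it, adjust the comparison for time since stroke and baseline score; where they do not, say so.

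The prospective data are already collected, so the cost is a few sentences and a small amount of analysis. The downside is wide intervals and a more modest claim. These steps reduce the problem but cannot fully separate recovery from treatment in a single group: a slope on time since stroke could reflect either natural recovery or a different response to treatment.
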